9.3 Primary Efficacy Endpoint(s) and Analyses

9.3.1 Primary Efficacy Endpoint(s)

The primary endpoint is the achievement of ACR50 at Week 12.

ACR criteria are commonly used standard criteria mentioned in the guidance of American College of Rheumatology to evaluate the effectiveness of investigation drug in RA clinical trials. It is a composite measurement calculated based on the improvement over a set of core measurements.

ACR50 is defined as at least 50% improvement (compared to baseline values) in tender and swollen joint counts and at least 50% improvement in 3 of the remaining 5 core set measures (patient's assessment of pain, patient's global assessment of disease activity, physician's global assessment of disease activity, HAQ-DI and hsCRP).

A subject will be classified as an ACR50 responder, if the following conditions are met:

1. $\geq 50\%$ improvement from baseline in tender joint count (TJC68) and
2. $\geq 50\%$ improvement from baseline in swollen joint count (SJC66) and
3. $\geq 50\%$ improvement from baseline in at least 3 of the following 5:
 - patient's assessment of pain (on a 0-10 NRS)
 - patient's global assessment of disease activity (PtGA) (on a 0-10 NRS)
 - physician's global assessment of disease activity (PhGA) (on a 0-10 NRS)
 - HAQ-DI
 - hsCRP

9.3.2 Analysis of Primary Efficacy Endpoint(s)

The statistical null hypothesis corresponding to the primary endpoint is that there is no difference between an ABBV-154 group and the placebo group response rate in the proportion of subjects achieving ACR50 at Week 12.

Analysis of the primary endpoint will be conducted in the ITT Population based on treatment as randomized using NRI-MI. Comparison of the primary endpoint will be made between each ABBV-154 group and the placebo group using the CMH test adjusting for Baseline glucocorticoid (yes/no), number of prior failed b/tsDMARDs (1; 2 or more), and a combined prior anti-TNF failure/adalimumab use factor (prior anti-TNF failure with adalimumab use; prior anti-TNF failure without adalimumab use; no prior anti-TNF failure)].

The attributes of the estimands corresponding to the primary efficacy endpoint are summarized in Table 1.

Table 1. Summary of the Estimand Attributes of the Primary Efficacy Endpoint(s)

Estimand Label	Attributes of the Estimand				Statistical Summary
	Treatment	Endpoint	Population	Handling of Intercurrent Events (IE)	
Primary: Composite Estimand	ABBV-154 vs. Placebo	Achievement of ACR50 at Week 12	All randomized subjects who received at least one dose of study drug (ITT Population)	IE: none considered	Difference between ABBV-154 and placebo in the proportion of subjects achieving ACR50 at Week 12

9.3.3 Sensitivity and Supplementary Analyses of the Primary Efficacy Endpoint(s)

A sensitivity analysis of the primary analysis of the primary efficacy endpoint will be conducted using the MI method for handling missing data.

An additional analysis will be conducted where the baseline definition for patient's assessment of pain, PtGA, PhGA, and HAQ-DI is updated to where values collected up to 7 days after the day of first dose may be considered for the baseline value.

A separate analysis may be performed in the ITT Population excluding subjects who have major protocol deviations in the Placebo-Controlled Period. The subject exclusion criteria for this analysis will be finalized before unblinding data for the Primary Analysis.

9.4 Secondary Efficacy Endpoints and Analyses

9.4.1 Secondary Efficacy Endpoints

The continuous secondary endpoints are, at Week 12,

- Change in DAS 28 (CRP) from Baseline: DAS28 (CRP) is a composite index to assess disease activity in RA patients using hsCRP measurement. The DAS28 (CRP) provides a score between 0.96 and 10, indicating how active the rheumatoid arthritis is at the time of measurement.
- DAS28 (CRP) is calculated based on Tender Joint Count, Swollen Joint Count, Patient's Global Assessment of Disease Activity (PtGA) (on a 0-10 NRS), and hsCRP (in mg/L).

$$\text{DAS28 (CRP)} = 0.56 \times \sqrt{\text{TJC28}^*} + 0.28 \times \sqrt{\text{SJC28}^{**}} + 0.36 \times \ln(\text{hsCRP}^{\&} + 1) + 0.14 \times \text{PtGA}^{\gg} + 0.96$$

* TJC28 refers to the Subject's total Tender Joint Count out of the provided 28 evaluated joints.

** SJC28 refers to the Subject's total Swollen Joint Count out of the provided 28 evaluated joints.

& hsCRP refers to the high-sensitivity C-reactive protein lab value. hsCRP unit in the DAS28 (CRP) equation is expressed as mg/L.

» PtGA refers to the Patient's Global Assessment of Disease Activity.

Where $\sqrt{}$ is square root and \ln is natural log.

- **Change in CDAI from Baseline:** CDAI is a composite continuous index to assess disease activity without using hsCRP measurement. It can be calculated based on TJC28, SJC28, Patient's Global Assessment of Disease Activity (PtGA) (on a 0-10 NRS) and Physician's Global Assessment of Disease Activity (PhGA) (on a 0-10 NRS). It can be derived as follows:
CDAI = TJC28 + SJC28 + PtGA + PhGA.
- **Change in the HAQ-DI from Baseline**

The categorical secondary endpoints are, at Week 12,

- **Achievement of ACR20 and Achievement of ACR70:** The definition is similar to ACR50 with at least 20% and 70% improvement, respectively
- **Achievement of LDA defined by DAS28 (CRP) ≤ 3.2**
- **Achievement of LDA defined by CDAI ≤ 10**
- **Achievement of clinical remission (CR) defined by DAS28 (CRP) < 2.6**
- **Achievement of CR defined by CDAI ≤ 2.8**

9.4.2 Analyses of Secondary Efficacy Endpoints

The statistical null hypothesis corresponding to the secondary endpoint is that there is no difference between an ABBV-154 group and the placebo group at Week 12 in terms of response rate for a categorical endpoint and change from baseline for a continuous endpoint.

Analysis of the secondary endpoint will be conducted in the ITT Population based on treatment as randomized. Comparison of the secondary endpoint will be made between each ABBV-154 group and the placebo group using:

- **For categorical variables:** CMH test based on NRI-MI adjusted by Baseline glucocorticoid (yes/no), number of prior failed b/tsDMARDs (1; 2 or more), and a combined prior anti-TNF failure/adalimumab use factor (prior anti-TNF failure with adalimumab use; prior anti-TNF failure without adalimumab use; no prior anti-TNF failure).

- For continuous variables: MMRM mentioned in Section 9.2

The attributes of the estimands corresponding to the key secondary efficacy endpoints are summarized in Table 2.

Table 2. Summary of the Estimand Attributes of the Secondary Efficacy Endpoints

For binary endpoint:

Estimand Label	Attributes of the Estimand				Statistical Summary
	Treatment	Endpoint	Population	Handling of Intercurrent Events	
Binary Secondary: Composite Estimand	ABBV-154 vs. Placebo	Achievement of each binary secondary endpoint respectively	All randomized subjects who received at least one dose of study drug (ITT Population)	IE: none considered	Difference in proportion of subjects achieving each binary secondary endpoint

For continuous endpoint:

Estimand Label	Attributes of the Estimand				Statistical Summary
	Treatment	Endpoint	Population	Handling of Intercurrent Events	
Continuous Secondary: Composite Estimand	ABBV-154 vs Placebo	Change from Baseline in each respective continuous secondary endpoint	All randomized subjects who received at least one dose of study drug (ITT Population)	IE: none considered	Difference in the mean change from Baseline in each continuous secondary endpoint

9.4.3 Sensitivity and Supplementary Analyses for Secondary Efficacy Endpoints

Not applicable.

9.4.4 Supportive Secondary Efficacy Endpoints and Analyses

Not applicable.

9.5 Additional Efficacy Analyses

The primary and all secondary efficacy variables will be analyzed at all visits assessed other than Week 12, including in the LTE periods, using methods mentioned above. At time of the Primary Analysis, NRI will be used after Week 12 for all binary endpoints.

In addition, other efficacy endpoints described in Section 3.3 will be analyzed at all visits assessed using the same methods as secondary endpoints.

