2.4 Sample Size Determination

The planned total sample size of 425 subjects (approximately 85 subjects per treatment group) provides at least 90% power to detect a 22% difference between ABBV-154 and placebo in ACR50 response rate at Week 12 (assuming a placebo ACR50 response rate of 13%), at a 2-sided significance level of 0.1 based on Chi-square test.

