4.0 Analysis Populations

The following population sets will be used for the analyses.

Intent-to-Treat (ITT) Population

The Intent-to-Treat (ITT) Population includes all randomized subjects who received at least one dose of study drug. The ITT Population will be used for all efficacy analyses. Subjects will be included in the analysis according to the treatment groups to which they are randomized.

Safety Population

The Safety Population in Placebo-Controlled Period (Safety_PC) includes all subjects randomized and received at least 1 dose of study drug in Placebo-Controlled Period. This population will be used for the safety analysis in the Placebo-Controlled Period.

The All ABBV-154 Treated Population (ALL_154) includes all subjects who receive at least 1 dose of ABBV-154 during the study. This population will be used to provide a comprehensive summary of safety.

For these safety populations (Safety_PC and ALL_154), subjects are assigned to treatment groups based on the treatments they receive during the majority of their drug exposure time in the analysis period for each subject in the respective safety population.

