9.0 Efficacy Analyses

9.1 General Considerations

All efficacy analyses will be conducted in the ITT Population. All tests will be 2-sided at an α level of 0.1.

The Primary Analysis will be performed after all ongoing subjects have completed the Placebo-Controlled Period, and the database has been locked. This will be the only and final analysis for the primary and secondary efficacy endpoints.

Unless otherwise specified, the categorical endpoints and continuous endpoints will be analyzed by Cochran-Mantel-Haenszel (CMH) and Mixed Model for Repeated Measures (MMRM), respectively, and the corresponding analyses are specified in Section 9.2.

Two of the baseline randomization stratification factors, prior anti-TNF failure and prior adalimumab use, will be combined into a single prior anti-TNF failure/adalimumab use factor (prior anti-TNF failure with adalimumab use; prior anti-TNF failure without adalimumab use; no prior anti-TNF failure) in the analysis methods. Other randomization stratification factors will be used without combination.

Unless otherwise specified, any subject who is randomized based on a wrong stratum will be analyzed according to the actual stratum the subject belongs to.

"Baseline" refers to the last non-missing observation before or on the day of the first administration of study drug or randomization if no study drug is given. Observations on the same day as the first administration of study drug will be considered for baseline, regardless of whether observation time (if available) was after the first administration of study drug time.

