9.2.2 Handling of missing data in Categorical Endpoints

- Non-Responder Imputation incorporating multiple imputation to handle COVID-19 and logistical problems (geo-political restrictions) (NRI-MI) will be the primary approach to handle missing data for categorical endpoints. The

NRI-MI will categorize any subject who does not have an evaluation during a pre-specified visit window (either due to missing assessment or due to early withdrawal from the study) as a non-responder for the visit. The only exceptions are: 1) when the subject is a responder both before and after the visit window, where the subject will be categorized as a responder for the visit, and 2) when the data is missing due to COVID-19 infection or logistical restriction, or logistical problems (geo-political restrictions), which will then be handled by Multiple Imputation. Subjects whose change/percent change from Baseline cannot be calculated because of a missing Baseline will be considered as a non-responder at all post-baseline visits in NRI-MI approach.

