9.2.4 Summary of Long-Term Efficacy

Long-term efficacy in the LTE periods will be summarized using the As Observed case approach by treatment sequence (ABBV-154 40 mg EOW, ABBV-154 150 mg EOW, ABBV-154 340 mg EOW, ABBV-154 340 mg E4W, ABBV-154 150 mg EOW re-randomized from Placebo, ABBV-154 340 mg EOW re-randomized from Placebo).

- **As Observed (AO):** The AO analysis will be used for the summaries of long-term efficacy, which will not impute values for missing evaluations, and thus a

subject who does not have an evaluation on a scheduled visit will be excluded from the AO analysis for that visit.

- NRI-MI and MMRM will be used to summarize selected categorical and continuous efficacy variables, respectively, for long-term efficacy.

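### Does NRI after Week 12 at the Primary Analysis count visits that are not yet due as non-response?

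*SAP*

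**What the plan says.** SAP 9.5 extends the efficacy analyses beyond Week 12: "The primary and all secondary efficacy variables will be analyzed at all visits assessed other than Week 12, including in the LTE periods". It then adds: "At time of the Primary Analysis, NRI will be used after Week 12 for all binary endpoints".

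The timing is set in SAP 9.1: "The Primary Analysis will be performed after all ongoing subjects have completed the Placebo-Controlled Period, and the database has been locked". Follow-up beyond Week 12 therefore differs between subjects at that cut, according to when they entered.

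Plain NRI has no definition of its own. The only rule is the one for NRI-MI in SAP 9.2.2. It assigns non-response where the subject "does not have an evaluation during a pre-specified visit window (either due to missing assessment or due to early withdrawal from the study"). There are two exceptions: a subject who responds both before and after the window, and data missing because of COVID-19 or geo-political logistics, which go to multiple imputation.

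On the denominator, SAP 4.0 says: "The ITT Population will be used for all efficacy analyses". SAP 9.2.4 describes the long-term summaries. Under As Observed, a "subject who does not have an evaluation on a scheduled visit will be excluded from the AO analysis for that visit". It also provides that "NRI-MI and MMRM will be used to summarize selected categorical and continuous efficacy variables, respectively, for long-term efficacy".

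**The concern.** At the Primary Analysis, an ongoing subject who entered late has no Week 24 evaluation, simply because Week 24 has not arrived. Neither exception in SAP 9.2.2 covers that subject, the efficacy population is all of ITT, and no passage limits the denominator to subjects who have reached the visit. A programmer who codes the rule as no record in the window, hence non-responder, would count that subject as a Week 24 failure.

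The reported rate would then be the true rate multiplied by the share of subjects who have reached the visit. The curve would fall over time whatever the drug does, and it would part from the As Observed curve with no explanation in the SAP. The sponsor's team is unblinded at this analysis, and the study is meant to inform Phase 3 dose selection, so a false loss of response could mislead.

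**Working it through.** **Inputs.** About 85 subjects per group, a difference of 22 points, and (SAP 2.4) "assuming a placebo ACR50 response rate of 13" per cent, which implies 13% + 22% = 35% on active drug. The 35% is a Week 12 planning figure, held constant here for illustration only. The documents give no enrolment duration, so 39, 52 and 78 weeks of uniform enrolment are assumptions.

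**The plan's own figure.** SAP 2.4 claims at least 90% power. With 85 per group, 13% against 35%, two-sided 0.1 and the pooled chi-square test, power is 96.2%, so the claim holds. The plan states no rate after Week 12, so there is none to reproduce.

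**Reading A: not-yet-due visits count as failures.** With enrolment uniform over *E* weeks and the cut when the last subject reaches Week 12, the share due at Week *w* is 1 − (*w* − 12)/*E*. The displayed rate is 35% × share.

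| Visit | *E* = 39 | *E* = 52 | *E* = 78 |
|---|---|---|---|
| Week 14 | 33.2% | 33.7% | 34.1% |
| Week 18 | 29.6% | 31.0% | 32.3% |
| Week 24 | 24.2% | 26.9% | 29.6% |
| Week 36 | 13.5% | 18.8% | 24.2% |
| Week 48 | 2.7% | 10.8% | 18.8% |

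For example, at Week 24 with *E* = 52: 1 − 12/52 = 0.769, and 0.769 × 35% = 26.9%. The number per group counted as failures only because of the calendar is 85 × (1 − share) = 26.2, 19.6 and 13.1 at Week 24 for the three enrolment lengths.

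Entry time should be similar across randomised groups. All groups then shrink by about the same factor: differences between them shrink too, but the ordering of doses is kept.

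**Reading B: not-yet-due visits are left out.** The denominator is the subjects due, so the displayed rate is 35% and the calendar bias is zero, provided withdrawn subjects are held to the same due date. The price is precision. With *E* = 52, 85 × share is 65.4, 45.8 and 26.2 at Weeks 24, 36 and 48. The 95% half-width, 1.96 × √(0.35 × 0.65/*n*), is 11.6, 13.8 and 18.3 points, against 10.1 with all 85.

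**Which reading the text supports.**
- The bracket in SAP 9.2.2 gives the causes of absence as a missed assessment or early withdrawal. An ongoing subject before the visit has done neither. The rule does not reach that subject, so no third exception is needed.
- SAP 9.2.1 lists the sources of missing data in the same spirit: missed visits or assessments, withdrawal, COVID-19 and geo-political logistics. A visit still in the future is not on the list, though the list is not closed.
- ITT does not fix the denominator at each visit. The As Observed analyses are also ITT analyses, and they drop subjects visit by visit.
- The protocol's Appendix A expands NRI-MI as non-responder imputation with multiple imputation added. Plain NRI is therefore most simply SAP 9.2.2 with the multiple-imputation step removed.

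SAP 9.5 and SAP 9.2.4 do not conflict. The NRI sentence in 9.5 applies only at the Primary Analysis. Section 9.2.4 describes long-term summaries in general and already places NRI-MI beside As Observed.

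**The case for a change.** The strongest case for a change is that an SAP should not leave a denominator to inference. The phrase about a missing assessment can be coded as any absent record, the exceptions are introduced as the only ones, and the wording about all visits assessed selects visits rather than subjects. Under that coding the loss at later visits is large: 35% would show as 18.8% at Week 36 with 52-week enrolment. One sentence and one derived flag would remove the doubt.

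Two parts of this stand. Plain NRI is not defined separately, and no sentence expressly excludes visits not yet due. The arithmetic is also right under reading A. But reading A has to pass over the bracket in the rule, and it yields a rate that no analyst would take for a response rate: with 52-week enrolment the share due at Week 78 is zero, so every group would show 0%. Programming that table would expose the error before anyone relied on it. Disagreement between NRI and As Observed rates is not a defect in itself, because the two differ by design whenever data are missing.

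**Conclusion.** The concern does not call for a change. The natural reading of SAP 9.2.2 leaves not-yet-due visits out and carries no calendar bias. The downward shift (35% shown as 24.2% to 29.6% at Week 24 for 39 to 78 weeks of enrolment) arises only if the stated causes of absence are ignored. It also rests on assumed uniform enrolment, a constant 35% rate and no further dropout.

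Even then, little depends on it. By the Primary Analysis every subject has completed Week 12 or withdrawn, so the Week 12 primary and secondary results and MCP-Mod are untouched; the MMRM results and As Observed summaries are also unchanged. After Week 12 there is no placebo group, protocol 7.4 plans descriptive summaries by treatment sequence, and no decision rule in either document uses the later NRI rates. A final analysis follows once all subjects have finished or withdrawn. What remains is a small gap in detail that the analysts can settle when specifying the tables.

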9.6 Dose-Response Modeling for ABBV-154

The dose-response relationship among ABBV-154 dose groups and the placebo group will be characterized for the primary endpoint using the Multiple Comparison Procedure - Modeling (MCP-Mod) method [Pinheiro 2006, Bretz 2005]. The summary level response rates based on the primary analysis approach above will be used, and ADDPLAN DF software will be used to perform the MCP-Mod analyses.

A set of 6 pre-specified standardized candidate dose-response models, as described in Table 3 will be utilized to examine the dose-response relationship. A statistically significant dose-response relationship will be declared if at least one model is identified by the MCP-Mod method to be statistically significant at two-sided $\alpha = 0.1$. The fitted dose-response curves will be presented graphically for all statistically significant models along with 95% confidence bands. The minimum effective dose (MED) will be identified for each statistically significant model based on the pre-specified clinical meaningful target of 22%. The weighted MED across all significant models will be calculated, with weight being the inverse of each candidate dose-response model AIC.

Table 3. Candidate Models

Model	$f(d, \theta)$ $d = \text{dose},$ $\theta = \text{Model Parameters}$	$f^0(d, \theta)$ Standardized Model	Initial Value(s) for Parameter(s)*
Linear	$E_0 + \delta d$	d	NA
Exponential	$E_0 + E_1 \left[\exp\left(\frac{d}{\delta}\right) - 1 \right]$	$\exp\left(\frac{d}{\delta}\right) - 1$	$\delta = 680$
Logistic	$E_0 + \frac{E_{max}}{1 + \exp\left(\frac{ED_{50} - d}{\delta}\right)}$	$\frac{1}{1 + \exp\left(\frac{ED_{50} - d}{\delta}\right)}$	$ED_{50} = 150, \delta = 64.5$
EMax	$E_0 + \frac{E_{max}d}{ED_{50} + d}$	$\frac{d}{ED_{50} + d}$	$ED_{50} = 83.9$
sigEMax	$E_0 + \frac{E_{max}d^h}{ED_{50}^h + d^h}$	$\frac{d^h}{ED_{50}^h + d^h}$	$ED_{50} = 150, h = 3.6$
Quadratic	$E_0 + \beta_1 d + \beta_2 d^2$	$d + \frac{\beta_2}{ \beta_1 } d^2$	$\delta = -0.001$

* For Exponential model, the initial value was determined based on the assumption that ABBV-154 340 mg EOW will achieve 95% of the maximum efficacy of ABBV-154. For Logistic, EMax, sigEMax, and Quadratic model, the initial values were determined based on the assumption that ABBV-154 340 mg EOW and ABBV-154 140 mg EOW will achieve 95% and 50% of the maximum efficacy of ABBV-154, respectively.

Steps of MCP-Mod:

1. Choose a candidate set of models as in Table 3.
2. Compute the optimum contrast for each model.
3. Use contrast test to find all significant models while preserving family-wise error rate (FWER).
4. Use all significant models to make inference about the weighted target dose of interest.

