4.2 Discussion of Study Design

Choice of Control Group

Placebo has been selected as the appropriate control group to evaluate the primary efficacy endpoints as double-blind, placebo-controlled study designs are generally acknowledged as standard for unbiased estimates of treatment differences. There is no anticipated medical risk for subjects randomized to placebo with background concomitant MTX for 12 weeks.

Appropriateness of Measurements

Standard statistical, clinical, and laboratory procedures will be utilized in this study. All efficacy and safety-related measurements are standard for assessing disease activity in subjects with RA. All clinical and laboratory procedures are standard and generally accepted.

Suitability of Subject Population

The mechanism of action of ABBV-154 has the potential to improve disease activity in RA subjects. While this is the first study to test ABBV-154 in RA subjects, safety results of ABBV-154 in healthy volunteers indicate no safety issues of concern and no dose limiting toxicity.

Selection of Doses in the Study

The dose selection in this study was informed by the safety, efficacy, PK, and pharmacodynamic results from a related ADC with the same mechanism of action (ABBV-3373) in a Phase 2a proof-of-concept study in bio-naïve RA patients on background MTX.

The 3 selected eow dosing regimens in this study (40 mg, 150 mg, and 340 mg SC) are reasonably separated across a wide dose range to cover the potential clinical efficacious doses and to enable a robust characterization of dose/exposure-response relationships for Phase 3 dose selection. In addition, the 340 mg SC e4w dose regimen was chosen to provide the optionality of an eow vs. e4w dosing frequency for future Phase 3 trials. All selected doses are within the range of single doses safely tested in the ABBV-154 First in Human Study (highest dose 600 mg intravenous) and are adequately covered by safety margins provided by chronic toxicology studies. Projected ABBV-154 and A-1677770 safety margins for the high dose of 340 mg SC eow are at least 24-fold and 10-fold, respectively, based on predicted ABBV-154 human exposures and the observed toxicokinetic data in the 26-week cynomolgus monkey study.

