One supplementary analysis for primary endpoints is to test a pre-specified set of dose-response models among ABBV-154 dose groups and the placebo group at Week 12 using the Multiple Comparison Procedure – Modeling approach (MCP-Mod). Details of this method will be provided in the SAP.

Summary and Analysis of Secondary Endpoints

Analysis of secondary efficacy endpoints will be conducted on the ITT Population based on treatment as randomized.

Summary and Analysis of Additional Efficacy Endpoints

Additional endpoints, as described in Section 3.3, will also be analyzed.

Subgroup Analysis for Efficacy

To evaluate the consistency of efficacy across demographic and other Baseline characteristics, the following subgroup analysis will be performed on the primary endpoint:

- Baseline glucocorticoid use (yes/no)
- Number of prior failed b/tsDMARDs (1; 2 or more)
- Prior use of failed anti-TNF (yes/no)
- Prior use of adalimumab (yes/no)
- Age (\leq median/ $>$ median)
- Sex (female/male)
- Race (white/non-white)

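### SAP 9.6 weights the model-averaged MED by 1/AIC, a rule that depends on the arbitrary level of the AIC and on a likelihood the SAP does not state (minor)

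*SAP*

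**What the plan says.** Protocol 7.4 makes the MCP-Mod analysis supplementary ("One supplementary analysis for primary endpoints is to test a pre-specified set of dose-response models") and leaves the details to the SAP.

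SAP 9.6 gives the data level ("The summary level response rates based on the primary analysis approach above will be used") and the program ("ADDPLAN DF software will be used to perform the MCP-Mod analyses"). For each significant model it finds the dose at which the fitted effect reaches the 22-point target. Then "The weighted MED across all significant models will be calculated", "with weight being the inverse of each candidate dose-response model AIC". The last of the listed MCP-Mod steps is "Use all significant models to make inference about the weighted target dose of interest".

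No other section of either document gives a different weight, says from which likelihood the AIC is computed, or gives a reason for 1/AIC. Protocol 4.2 says that the eow dose range was chosen "to enable a robust characterization of dose/exposure-response relationships for Phase 3 dose selection".

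**The concern.** AIC = −2 log L + 2k, where k is the number of parameters. Its level shifts with constants that have nothing to do with fit, such as whether normalising terms of the likelihood are kept. Adding one constant to every AIC leaves the comparison between models unchanged, but it changes every 1/AIC weight and so the weighted MED. If the ratio of two models' weights is to depend only on their AIC difference, the weight has to be exponential in AIC. The factor one half puts it on the likelihood scale: exp(−AIC/2) = L·exp(−k).

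The sentence therefore does not fix the estimate in advance. At stake is the one model-averaged dose that the SAP reports from its dose-response modelling.

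**Working it through.** **Starting point.** The plan states no AIC or weight that could be reproduced. Its design figure does reproduce: 85 per arm, 13% vs 35%, two-sided 0.1, gives power 96.2%, consistent with the stated floor of 90%.

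**Inputs from the documents.** Six models and their initial values (SAP Table 3); 22-point target (SAP 9.6); 85 per arm and 13% on placebo (SAP 2.4).

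**Assumed inputs.** Active-arm response rates; 340 mg e4w entered as 170 mg eow; ED50 up to 510, h from 0.5 to 10, exponential delta up to 680. The MED is the smallest dose up to 340 mg with a fitted effect of at least 22 points. At the assumed rates all six contrasts are significant (z 3.9 to 5.3, adjusted critical value 1.84).

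**Step 1: level dependence, no trial data needed.** For illustrative AICs of 470, 472, 476 and 480:
- 1/AIC weights: 0.252, 0.251, 0.249, 0.247.
- After subtracting 460 from each: 0.338, 0.282, 0.211, 0.169.
- Akaike weights, w_m = exp(−0.5(AIC_m − AIC_min)) / Σ exp(−0.5(AIC_k − AIC_min)): 0.702, 0.258, 0.035, 0.005 in both cases.

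**Step 2: degree of discounting.** Relative to the best model (AIC = a), a model d units worse keeps a/(a + d) under 1/AIC and exp(−d/2) under Akaike. For d = 10:
- a = 500: 500/510 = 0.980.
- a = 6: 6/16 = 0.375.
- Akaike: exp(−5) = 0.007.

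**Step 3: one data set, three likelihoods.** Assumed steep curve: 13/33/38/40/38% for placebo, 40, 150, 340 eow, 340 e4w. Weighted-RSS AIC = Σ(p − fit)²/v + 2k, with v = p(1 − p)/85.

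| Model | MED (mg) | AIC | 1/AIC weight | Akaike weight |
|---|---|---|---|---|
| Linear | 285 | 15.2 | 0.104 | 0.005 |
| Exponential | 305 | 19.0 | 0.083 | 0.001 |
| Logistic | 49 | 8.1 | 0.195 | 0.189 |
| EMax | 61 | 6.0 | 0.263 | 0.534 |
| sigEMax | 66 | 8.0 | 0.197 | 0.198 |
| Quadratic | 137 | 10.0 | 0.158 | 0.073 |

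- Weighted RSS: 1/AIC gives 29.6 + 25.3 + 9.5 + 16.0 + 13.0 + 21.6 = 115 mg; Akaike gives 66 mg; equal weights give 150 mg. Adding 5, 10 or 50 to every AIC moves the 1/AIC result to 125, 131 or 143 mg. Akaike stays at 66 mg.
- Full Gaussian likelihood on the same five rates: this only adds Σ ln(2πv) = −4.78 − 4.11 − 4.05 − 4.03 − 4.05 = −21.0 to each AIC. In table order they become −5.8, −2.0, −12.9, −15.0, −13.0, −11.0. The 1/AIC weights become 0.175, 0.507, 0.079, 0.068, 0.079, 0.093. The worst fit (exponential) takes about half the weight and the best (EMax) 7%. The weighted MED is about 230 mg; Akaike is still 66 mg.
- Subject-level binomial: AICs of about 509 to 531 give weights of 0.165 to 0.168 over six models. The weighted MED is 129 mg against 67 mg with Akaike; here the exponential fit does not reach the target and drops out.

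**Step 4: the SAP's own planning shapes.** Table 3 shapes at their initial values, scaled to +27 points at 340 mg eow, weighted-RSS AIC. The true MED is where the shape reaches 22 points; for linear, 340 × 22/27 = 277. RMSE is the root mean squared error against it in 600 simulated trials per shape, without the contrast-significance filter.

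| Shape | True MED | 1/AIC | Akaike | RMSE 1/AIC | RMSE Akaike |
|---|---|---|---|---|---|
| Linear | 277 | 276 | 277 | 51 | 52 |
| Exponential | 289 | 285 | 284 | 52 | 52 |
| Logistic | 236 | 257 | 260 | 46 | 49 |
| EMax | 158 | 188 | 172 | 64 | 71 |
| sigEMax | 211 | 231 | 235 | 43 | 46 |
| Quadratic | 241 | 254 | 257 | 51 | 55 |

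Outside EMax the gap is at most 4 mg here, and at most 8 mg when the binomial AIC is included. For EMax it is 16 mg, or 9 to 20 mg as the effect at 340 mg eow varies from +24 to +30 points. In the EMax simulations the bias is 19 mg with 1/AIC and 3 mg with Akaike; the standard deviations are 61 and 71 mg.

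**Step 5: steeper curves.** The steep curve puts 20/27 = 74% of the 340 mg effect at 40 mg. An intermediate curve (13/28/36/40/36%) puts 15/27 = 56% there. The Table 3 EMax shape puts (40/123.9)/(340/423.9) = 40% there. The intermediate curve gives 161 mg (1/AIC) against 132 mg (Akaike). RMSE favours 1/AIC for the intermediate curve (70 vs 79 mg) and Akaike for the steep one (80 vs 75 mg). With e4w entered as 120 or 220 mg, or left out, the gaps are 45 to 53 mg (steep) and 30 to 33 mg (intermediate).

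**The case against.** The strongest reply is about accuracy. A gap from Akaike weights is not an error unless Akaike is closer to the truth, and Step 4 shows that it generally is not: with positive weighted-RSS AICs, 1/AIC has equal or lower RMSE for all six Table 3 shapes. With five dose groups, sharper weights partly follow noise. This stands. A reader might infer that the stated rule gives a less accurate MED; under the plan's own planning shapes that is not supported. What remains is larger upward bias for EMax-type curves and lower accuracy for the steep curve.

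Second, with one program, one data set and one likelihood the weights are determinate, and nobody adds constants to AICs. That is true once the likelihood is fixed, but the SAP does not fix it. Step 3 shows that keeping or dropping a normalising constant is enough to move the result from 115 to about 230 mg. The favourable RMSE figures also hold only for one positive form of the AIC.

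Third, summary-level rates after NRI-MI are not plain binomial counts, so the near-equal weights of a subject-level binomial AIC may never arise. This is fair; the binomial case marks one end of a range.

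Fourth, the analysis is supplementary, and the SAP already calls for the MED of each significant model and the fitted curves, so the spread will be visible. This stands and limits the consequence.

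Fifth, how ADDPLAN DF forms its weights cannot be checked from the documents. If it already uses exponential weights, only the description is wrong.

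**Conclusion.** The rule is defective as written, and the point is minor. That 1/AIC weights depend on the AIC's level is algebra and needs no assumption. That they can be practically equal, partly discounting or reversed follows from the unstated likelihood.

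The size in mg rests on assumed response rates, e4w coding and parameter bounds. With positive AICs it is at most 8 mg for five of six Table 3 shapes, about 9 to 20 mg for EMax with the weighted-RSS AIC, and about 30 to 50 mg only for curves steeper than any planning shape.

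Two stronger readings should be resisted. The first takes a shift of 30 mg or more as the expected effect; it depends on curves that the SAP did not plan for or on a particular likelihood. The second supposes that the Phase 3 dose turns on this number; Protocol 4.2 names dose selection as the purpose of the dose range, but neither document ties a decision to the weighted MED. The CMH comparisons, contrast tests, fitted curves and per-model MEDs are unaffected.

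**What to change.** Replace the weighting sentence in SAP 9.6 with: weights w_m = exp(−0.5(AIC_m − AIC_min)) / Σ exp(−0.5(AIC_k − AIC_min)), the sum running over the significant models, with all AICs computed from one likelihood that the SAP names. Then confirm that the ADDPLAN DF output uses this formula. If it already does, the change only brings the sentence into line.

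The cost is one SAP sentence and one output check before unblinding, with no new data. The downside is that more discriminating weights can raise the variance somewhat with five dose groups (EMax standard deviation 71 against 61 mg in Step 4). A sponsor who prefers flatter weights for that reason could state equal weights openly, which are at least well defined.
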